#### 11.4.5.2. Other Safety

#### Vital signs

Vital signs (eg, pulse, blood pressure, and respiration rate) will be summarized by baseline and change from baseline to each scheduled assessment time with descriptive statistics.

#### Laboratory tests

Laboratory test results will be summarized by baseline and change from baseline to each scheduled assessment time with descriptive statistics.

Number and percentage of subjects with a potentially clinically significant value (PCSV) at any post-randomization time point will be summarized for each clinical laboratory test for all subjects and separately for subjects in whom the PCSV criterion was normal or missing at baseline.

Shift tables based on baseline normal/abnormal and other tabular and graphical methods may be used to present the results for laboratory tests of interest.

#### **Regeneron Pharmaceuticals, Inc.**

#### CONFIDENTIAL

Listings will be provided with flags indicating the out of laboratory range values.

#### 11.4.5.3. Treatment Exposure

This is a single dose study.

#### 11.4.5.4. Treatment Compliance

Treatment compliance will be assessed via the summary of treatment exposure as described in Section 11.4.5.3.

#### 11.4.6. Pharmacokinetics

#### 11.4.6.1. Analysis of Drug Concentration Data

The concentrations of total REGN5713, REGN5714, and REGN5715 over time will be summarized by descriptive statistics for each of the treatment groups.

No formal statistical hypothesis testing will be performed.

#### 11.4.7. Analysis of Immunogenicity Data

Immunogenicity will be characterized by the ADA response and titer observed:

- Pre-existing immunoreactivity, defined as a positive ADA assay response at baseline, with all post-dose ADA results negative, or a positive assay response at baseline, with all post-dose ADA assay responses less than 9-fold over baseline titer levels
- Treatment-emergent ADA response, defined as any post-dose positive ADA assay response when the baseline results are negative
- Treatment boosted ADA response, defined as any post-dose positive ADA assay response that is 9-fold over baseline titer levels when baseline is positive in the ADA assay
- Maximum ADA Titer values
  - Low (titer <1,000)
  - Moderate  $(1,000 \le \text{titer} \le 10,000)$
  - High (titer >10,000)

Listings of pre-existing, treatment-boosted, and treatment-emergent ADA responses, and ADA titers presented by subject, time point, and treatment group will be provided separately for REGN5713, REGN5714, and REGN5715. Incidence of treatment-emergent ADA will be assessed as absolute occurrence (N) and percent of subjects (%), grouped by treatment group and ADA titer level.

Plots of drug concentrations will be examined and the influence of ADA responses on individual PK profiles evaluated separately for REGN5713, REGN5714, and REGN5715. Assessment of impact of ADA responses on safety and efficacy may be provided.

**Regeneron Pharmaceuticals, Inc.** 

#### 11.4.8. Analysis of Pharmacodynamic and Exploratory Biomarker Data

The change and percent change from baseline in the birch skin prick test mean wheal diameters will be analyzed using an analysis of covariance (ANCOVA) model, with treatment, randomization stratification factors, visit and the treatment by visit interaction as factors in the model and the baseline mean wheal diameter as a covariate. Between group estimates comparing REGN5713-5714-5715 versus placebo will be presented for the end of study.

The prevalence of poly-allergy for tree homologue allergens and others being tested in this study will be assessed based on SPT and sIgE test results. The relationship between baseline SPT and sIgE of birch and homologue tree allergens will also be evaluated, as well as the correlation between SPT and sIgE and symptom scores. The within-subject variability in sIgE in and out of birch pollen season will also be evaluated.

# 11.5. Additional Statistical Data Handling Conventions

The following analysis and data conventions will be followed:

#### **Definition of baseline**

The last assessment before the administration of study drug on day 1 will be considered as the baseline evaluation.

#### Handling data in case of grass pollen season overlap with birch pollen season

Grass pollen season may start as birch pollen season is ending, thus potentially confounding allergic symptoms evaluated during the overlap of birch and grass pollen seasons. If birch pollen season overlaps with grass pollen season during this study, symptom and medication data collected from days after the start of the grass pollen season will be excluded from analyses.

#### General rules for handling missing data

If the start date of an AE or concomitant medication is incomplete or missing, it will be assumed to have occurred on or after the intake of study medication, except if an incomplete date (eg, month and year) clearly indicates that the event started prior to treatment. If the partial date indicates the same month or year of the intake of study medication date, then the start date by the study medication intake date will be imputed; otherwise, the missing day or month by the first day or the first month will be imputed.

No imputations for missing laboratory data, ECG data, vital sign data, or physical examination data will be made.

#### Visit windows

Assessments taken outside of protocol-allowable windows will be displayed according to the case report form (CRF) assessment recorded by the investigator.

#### Unscheduled assessments

Extra assessments (laboratory data or vital signs associated with non-protocol clinical visits or obtained in the course of investigating or managing AEs) will be included in listings, but not summaries. If more than 1 laboratory value is available for a given visit, the first observation will be used in summaries and all observations will be presented in listings.

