**Regeneron Pharmaceuticals, Inc.** 

	SCREENING PERIOD	TREATMENT P	ERIOD	F	OLLOW-	UP PER	IOD	
Study Procedure	Screening Visit 1 	Randomization Visit 2 	Visit 3 Tel.	Visit 4 Tel.	Visit 5 	Visit 6 Tel.	EOS/ET Visit 7 	Unscheduled Visit
Day	-84 to -7	1 	2	28 	57 	85	113 	
Window (Days)	+7	±3		±7	±14	±14	±14	
Laboratory Testing								
Hematology	X 				Х		Х	Х
Blood chemistry	X 				Х		Х	Х
Pregnancy test, urine (in WOCBP) 		X 		X 	Х	X 	Х	Х
Pregnancy test, serum (in WOCBP) 	Х							Х
Urinalysis	Х							Х
Serum total IgE		Х			Х		Х	
Serum sIgE for birch pollen and Bet v 1 and other regional or relevant allergens	Х	Х			X		Х	Х
Serum sIgE for concomitant and homologous allergens		Х			Х		Х	
Interference assay, serum		Х						
Pharmacokinetics and Immunogenicity			•	•	•			
PK 		X 			X		Х	Х
ADA 		X 					Х	Х
Biomarkers and Pharmacogenomics								
FBR samples, serum and plasma (optional) 		Х			Х		Х	
Genomic DNA sample (optional) 		X 						
ACQ-5=asthma control questionnaire-5; ADA=anti-	drug antibody; AE=	adverse event; DMS=	=daily me	dication s	core; ECC	G=electro	cardiogram;	EOS=end of
study; ET=early termination; FBR=future biomedica S=patient global impression of severity; PK=pharma immunoglobulin E; SPT=skin prick test; Tel=telepho potential.	l research; FSH=fo cokinetics; RQLQ one; TNSS=total na	llicle stimulating hor (S)=standardized rhin sal symptom score; 7	mone; PFA loconjunct COSS=tota	ASQ=poll tivitis qua ll ocular s	en food al lity of life ymptom s	lergy syn question core; WO	nptom quest naire; sIgE= CBP=wome	ionnaire; PGI- allergen-specific en of childbearing

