#### 9.1.1. Footnotes for the Schedule of Events Table

- Screening SPT for birch, birch homologous trees, and other common allergens will be performed as described in the study manual. Skin prick test for birch should be performed prior to other screening assessments. If screening SPT for birch is negative (ie, mean wheal diameter <5 mm greater than a negative control), then other screening visit procedures do not need to be performed as the subject will have failed screening (refer to Section 7.2.1 Inclusion Criteria, #3).
- 2. Randomization may occur within 1 day prior to study drug administration. All safety assessments performed at screening must be normal and checked against the inclusion/exclusion criteria prior to study drug administration.
- 3. The timing of in-clinic visits may vary for each study site, depending on the start, peak, and end dates of the local birch pollen season (as determined by local pollen counts; refer to Section 9.2.2). The randomization visit will be scheduled approximately 2 weeks before the start of birch pollen season, and the end of study (EOS) visit approximately 16 weeks after the randomization visit (depending on the duration of the local birch pollen season). In addition, visit 5 will be scheduled to occur within 2 weeks of the anticipated local peak of the birch pollen season.
- 4. If randomization occurs >60 days after the screening visit, medical history, blood chemistry, hematology, and spirometry must be repeated prior to randomization.
- 5. E-diary and rescue medications will be dispensed at the randomization visit. E-diary and any unused rescue medications will be returned at the EOS visit. Refer to Section 8.2 for more information on rescue treatments.
- 6. TNSS, TOSS, and DMS will be recorded daily via e-diary, starting at the randomization visit until EOS. Refer to Section 9.2.4.1, Section 9.2.4.2, and Section 9.2.4.4 for procedural details.
- 7. In asthmatic subjects, ACQ-5 scores will be recorded weekly via e-diary, starting from the randomization visit until EOS. Refer to Section 9.2.4.6 for procedural details.
- 8. In all subjects, RQLQ (S) scores will be recorded weekly via e-diary starting from the randomization visit until EOS. Refer to Section 9.2.4.7 for procedural details. In asthmatic subjects, the weekly RQLQ (S) and ACQ-5 assessments may be performed on the same day.
- 9. Refer to for Section 9.2.4.8 procedural details.
- 10. Refer to for Section 9.2.4.9 procedural details.

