5.7. Analysis of Safety Data

The analysis of safety and tolerance will be performed on the SAF, as defined in Section 3.2.

The safety analysis will be based on the reported AEs, clinical laboratory evaluations and vital signs.

Thresholds for treatment-emergent Potential Clinically Significant Values (PCSV) in laboratory variables and vital signs are defined in Appendix 10.3. Treatment-emergent PCSV is any PCSV developed or worsened in severity compared to the baseline during the treatment and follow-up period. The baseline when determining treatment-emergent PCSV refers to the baseline value of the study.

The time interval to detect any event or abnormality is between the first injection of study medication and EOS.

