6.4. Analysis Visit Windows

Data analyzed by-visit-analysis (efficacy [excluding daily diary data], laboratory data, vital sign) will be summarized by the study scheduled visits described in the study protocol and SAP "Schedule of Event".

The analysis visit windows are created per study Schedule of Events (SOE) table for each parameter and will be applied if the data from study scheduled visits are unavailable. The following general rules will be applied to unscheduled visit and/or early termination (ET) visit mapping for each parameter.

1. If ET visit falls in an analysis window which already has non-missing observed value of this parameter from the scheduled visit, ET will be mapped to the next scheduled visit.

CONFIDENTIAL

Page 39 of 56

- 2. If both ET visit and unscheduled visit of the same parameter are available in the same analysis visit window, only ET visit will be mapped.
- 3. If multiple unscheduled visits of the same parameter are available in the same analysis visit window, the unscheduled visis will be mapped using the following rules:
 - a. The closest unscheduled visit from the target day will be selected
 - b. If multiple unscheduled visits exist on the same day, the first unscheduled visit will be used.
- 4. If mapping distance is greater than 4 weeks, the unscheduled visit will not be mapped.

Unscheduled visits and early termination (ET) visit will be mapped per the following analysis visit windows based on the study day/visit of each parameter.

Visit from SOE	Target Study Day*	PFASQ, SPT	PGI-S
Baseline	1	≤1	≤ 1
Visit 5	57		[2, 85]
Visit 7 (EOS)	113	≥ 2	≥ 86

Analysis Visit Window for Efficacy Endpoints

*Study days are calculated from the day of 1^{st} injection. Study day = (date of assessment -1^{st} injection date +1) when date of assessment $\ge 1^{st}$ injection date; otherwise study day = (date of assessment -1^{st} injection date). If subject never received any dose of study drug, randomization date will be used in the place of 1^{st} injection date.

Visit from SOE	Target Study Day*	Vital Sign	Physical Exam	Laboratory#, PK	ADA	Serum total IgE, Serum sIgE for birch pollen and Bet v 1 and other regional or relevant allergens, Serum sIgE for concomitant and homologous allergens
Baseline	1	≤ 1	≤ 1	≤ 1	≤ 1	≤ 1
Visit 5	57	≥2		[2, 85]		[2, 85]
Visit 7 (EOS)	113		≥2	≥86	≥2	≥86

Analysis Visit Window for Safety and Biomarkers

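### Protocol 11.5 keeps unscheduled and AE-driven laboratory and vital-sign values out of summaries, which conflicts with the PCSV counts promised in Protocol 11.4.5.2 and SAP 5.7; the SAP never says which values count

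*Protocol*

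**What the plan says.** Protocol 11.5 (Unscheduled assessments) covers laboratory data and vital signs from visits outside the protocol schedule or "obtained in the course of investigating or managing AEs) will be included in listings, but not summaries". For repeats it adds: "If more than 1 laboratory value is available for a given visit, the first observation will be used in summaries".

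Protocol 11.4.5.2 (Laboratory tests) says: "Number and percentage of subjects with a potentially clinically significant value (PCSV) at any post-randomization time point will be summarized". SAP 5.7 defines a treatment-emergent PCSV as one that develops or worsens against baseline during treatment and follow-up, and adds: "The time interval to detect any event or abnormality is between the first injection of study medication and EOS". It does not repeat the exclusion of unscheduled values. SAP 5.7.2 and 5.7.3 place the PCSV counts in their lists of laboratory and vital-sign summaries.

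SAP 6.4 deals with data analysed by visit. It lets early termination (ET) and unscheduled values stand in for a scheduled value that is unavailable, with a limit: "If mapping distance is greater than 4 weeks, the unscheduled visit will not be mapped". SAP 1.2.3 lists one change from the protocol's statistical section, the removal of the per-protocol set.

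**The concern.** A PCSV table answers a simple question: how many subjects in each arm crossed a threshold at any time after dosing? Values prompted by illness, or by an abnormal result that needs repeating, are among the most likely to cross one. Protocol 9.1.3 gives repeat testing and adverse event follow-up as reasons for unscheduled visits, and Protocol 9.2.7.1 requires significantly abnormal post-treatment results to be repeated. Protocol 11.5, read literally, removes these values from the count.

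Two programmers could each claim to follow the plan and produce different safety tables. The one following Protocol 11.5 could miss early or transient abnormalities. The first-observation rule adds to this, because a worse repeat at the same visit would not be the value summarized.

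**Working it through.** The plan gives no figure to reproduce. The check is a comparison of rules followed by day arithmetic.

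**1. Do the rules conflict?** Take a laboratory value drawn on day 20 to investigate an adverse event.

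| Source | Does it enter the PCSV count? |
|---|---|
| Protocol 11.5 | No: listings only |
| Protocol 11.4.5.2 | Yes: the count covers all time after randomization |
| SAP 5.7 | Yes on its face: it lies between first injection and end of study (EOS) |
| SAP 5.7.2, 5.7.3 | Not stated; the PCSV count is called a summary, which is what Protocol 11.5 governs |

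**2. When are scheduled values taken?** (Protocol Table 1)
- Hematology and chemistry after dosing: Visit 5, 57 − 14 = 43 to 57 + 14 = 71; EOS/ET, 113 − 14 = 99 to 113 + 14 = 127.
- Vital signs after dosing: 2 hours after injection, then Visit 5.

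For a subject who stays in the study, the nominal windows leave days 2–42 with no scheduled hematology or chemistry. The timing is nominal because "visit 5 will be scheduled to occur within 2 weeks of the anticipated local peak of the birch pollen season".

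**3. What can SAP 6.4 recover for by-visit data?** The laboratory window for Visit 5 is days 2–85 and the target is day 57. With the 28-day limit, 57 − 28 = 29 and 57 + 28 = 85. An unscheduled value can therefore stand in for Visit 5 only from day 29 to day 85, and only if the scheduled value is unavailable. An unscheduled value on days 2–28 is at least 57 − 28 = 29 days from target and cannot be mapped to Visit 5. The limit names unscheduled visits only, so an ET draw on day 20 can be mapped there.

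**4. Example.** ALT is normal at baseline, 12 × ULN at an unscheduled day-20 draw, and normal by day 57. It meets the SAP 10.3 level of above 10 and up to 20 × ULN with baseline at or below 10 × ULN. Under SAP 5.7 it counts; under Protocol 11.5 it does not.

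**5. How much could scheduled draws catch?** This is an illustration. Assume onset is uniform over days 2–56 (55 days) and the episode lasts d days. With the Visit 5 draw on day v, the proportion caught is the number of onset days s from 2 to 56 with s ≤ v ≤ s + d − 1, divided by 55.

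| Visit 5 draw | d = 7 | d = 14 | d = 28 |
|---|---|---|---|
| Day 43 | 7/55 = 13% | 14/55 = 25% | 28/55 = 51% |
| Day 57 | 6/55 = 11% | 13/55 = 24% | 27/55 = 49% |
| Day 71 | 0% | 0% | 13/55 = 24% |

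The EOS draw adds nothing here: the latest such episode ends on day 56 + 28 − 1 = 83, before day 99. The remainder (89%, 76% and 51% for a day-57 draw) is a ceiling on what the exclusion could drop, because some episodes would never be sampled at all.

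**The case against.** The strongest reply is that the PCSV-specific text prevails. SAP 5.7 counts any PCSV from first injection to EOS with no carve-out, and Protocol section 11 describes itself as the basis for the SAP. SAP 6.4 already admits some unscheduled values, so the SAP has moved away from a strict reading of Protocol 11.5. Unscheduled visits also have their own column in Table 1, so they might be called protocol visits.

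This stands as far as showing that the loss is not certain. It does not settle the matter. No text says that SAP 5.7 overrides the exclusion, and the adverse event clause in Protocol 11.5 applies whether or not the visit counts as a protocol visit.

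A reader might infer more than the documents support:
- **That the tables will miss these values.** That follows only if Protocol 11.5 is applied to them.
- **That silence in SAP 1.2.3 proves the rule survives.** The list is not complete: the Wilcoxon supportive analysis has been dropped, and the treatment-emergent ADA definition now includes a missing baseline. Neither change is listed there.
- **That no laboratory value on days 2–28 can be used.** ET draws can be, and SAP 6.4 governs by-visit data, not a whole-period count.
- **That any low blood pressure at an early unscheduled visit is a lost PCSV.** SAP 10.3 requires systolic pressure of 95 mmHg or less and a fall of at least 20 mmHg. A reading of 85 mmHg qualifies only with a baseline of at least 105 mmHg.
- **That PCSVs are the main safety screen, or that bias always favours one arm.** The safety endpoint is the incidence of TEAEs and serious TEAEs, and the documents give no event rates by arm.

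The values also stay in listings. Protocol 10.1.1 has isolated abnormal findings reported as adverse events if symptomatic, if they need corrective treatment, or on investigator judgment. That route will capture some of them, but it does not supply the threshold count that Protocol 11.4.5.2 promises.

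**Conclusion.** The point holds as a conflict between stated rules that the SAP leaves open. Followed literally, Protocol 11.5 can make the PCSV tables miss early or transient laboratory and vital-sign abnormalities. For a given criterion counted independently, leaving out qualifying values can lower the number of subjects but cannot raise it.

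The size cannot be estimated from the documents, because it depends on how often unscheduled values are taken and how often they cross a threshold. The catch rates above rest on an assumed uniform onset and assumed durations, and the day ranges rest on nominal visit timing. Efficacy inference, sample size and power are not affected. The wording should be settled before database lock, while the choice is still blind to treatment.

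**What to change.** - **SAP 5.7.2 and 5.7.3:** state that treatment-emergent PCSVs are derived from all post-dose values up to EOS (scheduled, unscheduled, repeat and ET), using the worst value for each criterion.
- **Protocol 11.5:** limit both the exclusion from summaries and the first-observation rule to by-visit descriptive statistics.
- **SAP 1.2.3:** declare the change.

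The cost is a sentence or two in each place and a programming flag. The values are already collected and listed, so no new data are needed.

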## 11.6. Interim Analysis

No formal interim analysis will be conducted.

# **11.7.** Statistical Considerations Surrounding the Premature Termination of a Study

If the study is terminated prematurely, only those parameters required for the development program and/or reporting to regulatory authorities will be summarized. Investigator and Sponsor responsibilities surrounding the premature termination of a study are presented in Section 15.1.

# **12.** QUALITY CONTROL AND QUALITY ASSURANCE

In accordance with ICH E6, the Sponsor is responsible for quality assurance to ensure that the study is conducted and the data generated, recorded, and reported in compliance with the protocol, GCP, and any applicable regulatory requirement(s). The planned quality assurance and quality control procedures for the study are described in this section.

# 12.1. Data Management and Electronic Systems

#### 12.1.1. Data Management

A data management plan specifying all relevant aspects of data processing for the study (including data validation [quality-checking], cleaning, correcting, releasing) will be maintained and stored at Regeneron (Sponsor).

A medical coding plan will specify the processes and the dictionary used for coding. All data coding (eg, AEs, baseline findings, medication, medical history) will be done using internationally recognized and accepted dictionaries.

The CRF data for this study will be collected with an electronic data capture (EDC) system, Medidata Rave.

#### 12.1.2. Electronic Systems

Electronic systems that may be used to process and/or collect data in this study will include the following:

- IVRS/IWRS system randomization, study drug supply
- EDC system data capture Medidata Rave
- Statistical Analysis System (SAS) statistical review and analysis
- Pharmacovigilance safety database
- Electronic diary and tablet for collection of patient-reported outcomes data

# 12.2. Study Monitoring

#### 12.2.1. Monitoring of Study Sites

Regeneron uses a study-specific risk-based approach to study monitoring and oversight, aligned with risk-based quality principles, outlined in ICH E6 (R2) Guideline for Good Clinical Practice. Risk-Based Quality Monitoring (RBQM) methodology focuses on employing a fit-for-purpose monitoring strategy, supported either directly by Regeneron as Sponsor, or via our CRO partners. RBQM strategies include: reduced source data verification (SDV), targeted source data review (SDR), the use of off-site/remote and triggered on-site monitoring visits, and Centralized Monitoring to identify site level risks and study level trends. The investigator must allow study-related monitoring activities to occur.

The study monitors will perform ongoing source data review to verify that data recorded in the CRF by authorized site personnel are accurate, complete, and verifiable from source documents, that the safety and rights of subjects are being protected, and that the study is being conducted in accordance with the current approved protocol version and any other study agreements, ICH GCP, and all applicable regulatory requirements.

